1.4 Anticipated duration of the clinical investigation

The total duration of the clinical investigation is expected to be approximately 4 weeks: 2 weeks randomized to one arm of the study and 2 additional weeks with access to both websites.

2.0 CLINICAL PROTOCOL

2.1 Protocol number and title

STUDY00011578: Lung Transplant READY (Resources for Education and Decision-making for Your CF) Pilot Study

[figure not shown]
2.3 Study design

2.3.1 General study design

This is a prospective, multi-center, randomized, controlled single-blind rollover pilot study

2.3.2 Study design schematic

Figure 1: The study will last four weeks with a total of three study sessions including the following: Baseline Session (V1), 2-Week Follow-up Session (V2), and 4-Week Follow-up Session (V3).

2.4 Subject selection

2.4.1 General characteristics of the proposed subject population(s)

Study subjects will be volunteer CF patients, age 18 years or above with FEV₁ of less than 50% predicted and have not yet undergone LTx. Approximately 50 subjects who give informed consent, meet all of the inclusion criteria and none of the exclusion criteria will be enrolled in the study.

LTx is an option for treating end-stage lung disease in CF. The population of CF patients with FEV₁ less than 50% represents a subset of individuals living with CF who are closer to the stage where LTx might become a viable option. These patients are the ones most likely to benefit from access to ToT, making them a relevant and representative group for this investigation. Additionally, individuals with low socioeconomic status have historically limited access to lung transplant and worsened outcomes. We aim to include individuals considered to be from “communities of concern” as a minimum of 30% of our study population. The “communities of concern” will be individuals who are racially

minoritized, Hispanic ethnicity, Medicaid insurance status (primary or secondary), and/or a high school education or less.

2.4.2 Anticipated number of research subjects

The study will enroll approximately 50 adults with CF and an FEV₁<50% predicted, without prior LTx. Individuals will be recruited from the University of Washington and collaborating adult CF centers across the United States.

We anticipate 90% (45 participants) of enrolled participants will complete the 2-week study visit.

2.4.3 Inclusion criteria

1. Diagnosis of CF
2. Adult, greater than or equal to 18 years of age
3. Able to read and understand English, but English can be a second language
4. FEV₁ <50% predicted

2.4.4 Exclusion criteria

1. Previously underwent LTx

2.5 Study procedures

2.5.1 Screening procedures

Research coordinators and lead researchers at the University of Washington (UW) Adult Cystic Fibrosis Clinic will conduct eligibility screening by utilizing the Cystic Fibrosis Patient Registry database (PortCF), medical records, and clinic schedules. Eligible individuals will be contacted before their clinic appointments, with study information provided via phone, and consent forms offered through mail or email.

Additionally, in STUDY0007475 approved by the UW HSD IRB, participants will be distributed a screening survey which provides the ability to voluntarily opt-in to being contacted by the UW research team for additional opportunities to participate in related studies. Collaborators at external sites will screen their local PortCF registry for participants meeting eligibility criteria and advertise the availability of the screening survey. CF patients consent separately to participate in the CFF registry which allows for screening for research study eligibility. The screening survey will be advertised to eligible participants at collaborating CF centers which allows for the recruitment of participants from within and outside of the UW to enable generalizable results. Per HHS guidelines, collaborating sites were considered not engaged in the research and did not require site-IRB approval to advertise the availability of this screening survey.

Individuals recruited from STUDY0007475 who opt-in to being contacted by the UW research team will be contacted to participate in this study. Study staff at the UW will call the patient and provide detailed information about the study. UW study staff will provide informed consent over the phone and the patient will provide verbal consent to participate. The UW research coordinator will mail or email copies of the consent form for participants to keep for their records.

2.5.2 Study procedures

The study will last four weeks with a total of three study sessions including the following: Baseline Session (V1), 2-Week Follow-up Session (V2), and 4-Week Follow-up Session (V3). All study visits will occur remotely via Zoom videoconferencing.

Study procedures will include the following:

Surveys – Participants will be asked to complete surveys at each study session. Surveys may consist of the following instruments: PrepDM Scale[1], Decisional Conflict Scale[6], Shortened Test of Functional Health Literacy in Adults (S-TOFHLA)[5], questions from the Health Information National Trends Survey (HINTS)[7], assessment of health numeracy[8], GAD-7[9], an investigator-designed lung transplant knowledge assessment, System Usability Scale (SUS)[10], general satisfaction scale, Hospital anxiety and depression scale (HADS)[11], PHQ-9[12], Cystic Fibrosis Questionnaire – Revised (CFQ-R)[13], Acceptability of Intervention Measure (AIM)[14], Intervention Appropriateness Measure (IAM)[14], and Feasibility of Intervention Measure (FIM)[14]. Each set of surveys will take approximately 15-20 minutes to complete.

Interview – Interviews will take place at each study session, via Zoom teleconferencing. Interviews will take approximately 30-60 minutes. All interviews will be recorded and transcribed for qualitative analyses. The research team will use an interview guide with directed questions discussing topics including shared decision making and general feedback on ToT and the attention control website (unos.org) including perceptions of and experience with using the resources, and any barriers to ongoing use of the research website. Structured interviews on the day of the baseline session may also address preparedness to discuss LTx, ask participants to describe the most impactful aspect of the research websites, and summarize the ‘CF Story’ that was most meaningful.

Research website – Participants will be introduced to the research website during the baseline session (V1). The research website is a portal that will contain links to two interventions including ToT and an attention control (unos.org). Before accessing the research website during the baseline session, participants will be randomized to first receive access to only one of the two websites through the portal. The research website will track website usage (i.e. time spent, content accessed, etc.) for all study participants for both ToT and unos.org. Once the participant completes the 2-week study visit (V2), the portal will contain access to both ToT and unos.org for the remainder of the study (2 more weeks).

2.5.3 Allocation to treatment arms

Participants will be randomized 1:1 to either the intervention (“Take on Transplant”) or the attention control (unos.org), stratified by $FEV_1 < 30\%$ versus 30-50%. Participants will be given access to their assigned website via the research website portal for two weeks. After the 2-week session interview, access to the opposite arm assignment will be unlocked and participants will have unlimited access to both the intervention (ToT) and the attention control (Unos.org).

2.5.6 Withdrawal of subjects

Subjects can withdraw at any point in time. They will be given contact information of the study staff if they decide they would like to withdraw or if they have any questions pertaining to their involvement in the study.

2.5.8 Procedures to assess safety

We will assess safety using the PHQ-9[12] and GAD-7[9] survey assessments.

The topic of LTx can be distressing to some with CF. There could be a risk of increasing depression symptoms and/or suicidality through the introduction of LTx education in this patient population. The PHQ-9 and GAD-7 surveys will be administered at the baseline visit (V1) and at both study visits (V2, V3) after patients gain access to ToT or unos.org to assess whether introduction of transplant education has a negative psychological impact on patients including an increase in anxiety, depression, and/or distress. Patients with an abnormal PHQ-9 or GAD-7 will be allowed to enroll in the study because depression and anxiety are prevalent in advanced CF lung disease. We hypothesize use of ToT may actually lessen patients' depression and/or anxiety with time.

The interviewer (UW research staff) will review PHQ-9 responses immediately after responses are submitted. The interviewer will also probe, via discussion with the participant, for any indicators of negative psychological impacts of use of the decision support tool. If possible suicidality is endorsed on the PHQ-9 (positive response to question #9), the interviewer will provide a subject who endorses possible suicidality with the National Suicide Hotline phone number and will inform them to call the National Suicide Hotline if they need help prior to receiving the call from [name] or another study physician about the PHQ-9 results. Additionally, the PI, or another study physician, will be notified immediately after the abnormal PHQ-9 result is entered. The patient's CF clinician will be contacted directly immediately via secure communication, by the PI, in the setting of possible suicidality. The PI or another study physician will call the patient within 8 hours of a PHQ-9 response that indicates suicidality and the Columbia-Suicide Severity Rating Scale (C-SSRS) screen with triage points for primary care will be completed. The C-SSRS response protocol will be followed and a safety contract will be established with the patient by the physician by phone. [name], and the other study physicians, are trained physicians, practicing medicine in populations with advanced diseases, end of life concerns, and high rates of mental illness. [name] has clinical experience with patients who report suicidality and has the resource of a trained CF mental health specialist for complex cases.

2.5.9 Schedule of study visits and compensation

Intro Session	2-Week Session	4-Week Session
Interview \$40/hr. ~ 60 minutes	Interview \$40/hr. ~30 minutes	Interview \$40/hr. ~60 minutes
Survey \$10 – 20 minutes	Survey \$10 – 20 minutes	Survey \$10 – 20 minutes
Unlimited Research Website Access - \$160		

2.6 Study outcome evaluations

2.6.1 Study endpoints

Primary endpoints

- The co-primary endpoint is feasibility, which will be defined as successful by 90% of enrolled participants completing the 2-week study visit.
- The co-primary endpoint is an intention-to-treat assessment of the difference in mean PrepDM Scale in the intervention versus control arms of the study at the 2-week study visit.

Secondary endpoints

- Difference in mean confidence-weighted true false (CTF) knowledge score will be measured in the intervention versus control arms of the study. CTF scoring adds points for certainty in correct responses and deducts points for certainty in incorrect responses. Participants receive +2 points when "sure" about a correct response, +1 if unsure about a correct response, -1 if unsure about an incorrect response and -2 if sure about an incorrect response. For a 14-item knowledge test, the maximum score is +28 and the minimum score is -28, with higher scores indicating more knowledge about lung transplant.
- Decisional Conflict Scale change will be measured from the baseline study visit to the 2-week study visit. The intention-to-treat analysis will compare mean change in the Decisional Conflict Scale between the intervention and control arms of the study. Scores range from 0 [no decisional conflict] to 100 [extremely high decisional conflict].
- Likert rating of preparedness will be measured at the 2-week study visit (0=Don't know, 1= Not at all prepared, 2 = A little prepared, 3 = Moderately prepared, 4 = Very prepared). The intention-to-treat analysis will compare mean Likert-scale rating between the intervention and control arms of the study.
- PHQ-9 is a scale that measures symptoms of depression in the prior 2 weeks on a 0-27 scale, with higher scores indicating worsening depression and a score of 10 or higher consistent with a diagnosis of depression. Investigators will assess the difference in mean PHQ-9 score in the intervention versus control arms of the

study at the 2-week study visit. Investigators will also determine the proportion with new PHQ-9 score greater than or equal to 10 in each arm.

- GAD-7 is a scale that measures symptoms of anxiety in the prior 2 weeks on a 0-21 scale, with higher scores indicating worsening anxiety and a score of 10 or higher consistent with a diagnosis of generalized anxiety disorder. Investigators will assess the difference in mean GAD-7 score in the intervention versus control arms of the study at the 2-week study visit. Investigators will also determine the proportion with new GAD-7 score greater than or equal to 10 in each arm.
- Longitudinally characterize time spent using Take on Transplant through analysis of patient-level usage data. Average time spent using the research website from baseline to 2 weeks will be compared across study arms. Further, time spent using the investigator-designed website will be assessed as a predictor of: 1. change in CTF knowledge about LTx (14-question investigator-designed survey) from baseline to 2-week study visit, 2. change in Likert preparedness from baseline to 2-week study visit, 3. change in Decisional Conflict Scale from baseline to 2-week study visit, and 4. mean PrepDM Scale at 2-weeks.
- The PrepDM Scale will be measured for all participants with respect to Take on Transplant and mean score will be compared for participants in the intervention (4 weeks of exposure) versus control arms (2 weeks of exposure). PrepDM scores range on a scale from 0 to 100 with higher scores indicating a higher perceived level of preparation for decision making.
- Identify baseline demographic and health literacy predictors of increased tool usage.

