RATIONALE	
 1. Despite therapeutic advances in CF care, many CF patients will go on to require LTx, including individuals already affected by advanced lung disease, those for whom highly effective CFTR modulators are not available or not tolerated, and for some despite CFTR modulators. Individuals with CF seek information about LTx and feel underprepared for the LTx decision. Use of a decision support tool or online educational materials about LTx may improve the quality, efficiency and effectiveness of LTx education in CF clinic and empower patients to engage in discussions about this complex medical treatment by increasing their sense of preparedness for the discussion. Feasibility must be established. The Preparation for Decision Making (PrepDM) Scale[1] is a validated measure of preparedness for decision making with known variance and high internal consistency (a 0.92-0.96), but it has not been studied in the CF population. Individual questions within the PrepDM Scale are informative and reflect IPDAS process measures[2, 3]. It is unclear whether there are ceiling or floor effects for particular questions within the PrepDM scale when evaluating a LTx decision support tool in the CF population, and the proposed pilot study utilizing a test-retest approach will establish preliminary means standard deviations, and reliability in this population. A prior decision aid for LTx in CF was shown to decrease decisional conflict in a randomized clinical trial and we will assess change in the Decisional Conflict Scale as a secondary endpoint.[4] 2. Engagement with Take on Transplant over time allows users to explore the content, potentially viewing more 'CF Stories', 'Resource Library', and 'Frequently Asked Questions' content and more interactions with 'My CF Stage'. Shared decision-making may naturally appeal to and benefit individuals who seek out health-related information, feel empowered to advocate for their own needs, and have more advanced educational attainment, while potentially increasing disparities for patients who are already disadvantaged. Shared decision making interventions

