2.6.3 Statistical analysis plan

Primary endpoints

The co-primary endpoint is feasibility, which will be defined successful by 90% of enrolled participants completing the 2-week study visit (V2). Descriptive statistics will be used to determine whether this threshold was met.

The co-primary endpoint of difference in PrepDM scale score (Difference = intervention – control) at 2-weeks will be assessed using linear regression, with statistical significance level set at 2-sided alpha <0.05.

Secondary endpoints

Continuous secondary endpoints will be assessed using linear regression, with statistical significance level set at 2-sided alpha <0.05.

Categorical secondary endpoints will be assessed using Pearson's chi-squared test of independence, with statistical significance level set at 2-sided alpha <0.05.

Graphical methods and descriptive statistics will be used to evaluate differences in usage during the 4 weeks of access across subsets of the cohort with different socioeconomic

status (based on insurance status, income, education level) and health literacy (based on S-TOFHLA). Exploratory models will test for a dose-response relationship by 1) time spent using the tool (uses/week) and 2) number of ‘CF Stories’ viewed and PrepDM Scale at 2-week and 4-week study visits. Linear regression may be used to determine whether predictors of increased time spent using the tool can be identified from baseline demographics and questionnaire results. Subgroup analyses will compare changes across instruments among participants with adequate health literacy to those with inadequate or marginal health literacy. We will also perform subgroup analysis for patients with $FEV_1 < 30\%$ predicted.

These data will inform the feasibility of completing a larger, multicenter, randomized controlled trial of ToT and will inform duration of the larger trial.

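### The models relating website use to outcome name no baseline covariate, so their slopes can be biased, in a direction the documents do not settle

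*Combined protocol and SAP*

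**What the plan says.** Use is not assigned. Section 2.5.3: "Participants will be given access to their assigned website via the research website portal for two weeks". How much each person uses the site in that time is left to the person.

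Section 2.6.1, repeated in the synopsis, lists four use-outcome analyses among the secondary endpoints. The first is: "time spent using the investigator-designed website will be assessed as a predictor of: 1. change in CTF knowledge about LTx". The second is change in Likert preparedness, and the list ends: "3. change in Decisional Conflict Scale from baseline to 2-week study visit, and 4. mean PrepDM Scale at 2-weeks".

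For the method, section 2.6.3 says: "Continuous secondary endpoints will be assessed using linear regression, with statistical significance level set at 2-sided alpha <0.05". A separate sentence there adds: "Exploratory models will test for a dose-response relationship by 1) time spent using the tool (uses/week) and 2) number of" CF Stories viewed, against PrepDM at the 2-week and 4-week visits. Neither sentence names a covariate.

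The Rationale in the synopsis says: "Shared decision-making may naturally appeal to and benefit individuals who seek out health-related information", and continues with those who "have more advanced educational attainment, while potentially increasing disparities for patients who are already disadvantaged". It adds that measuring health literacy could help explain both differences in use and change in PrepDM. In the analysis section, baseline characteristics appear only as possible predictors of use ("Linear regression may be used to determine whether predictors of increased time spent using the tool can be identified from baseline demographics") and as subgroups.

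**The concern.** Randomisation protects the comparison between arms. It does not protect a slope on time used within an arm. Two routes to bias are open.

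- **A common cause.** If health literacy, education or information seeking raises both use and the outcome, use and outcome are correlated even when use does nothing. The Rationale raises this possibility, yet the planned models do not include these factors.
- **A change score without its baseline.** Change equals follow-up minus baseline, so it is usually negatively correlated with baseline. If use is related to the baseline score in either direction, it becomes related to change without any effect of use.

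The stake is limited but real. Four of these models are listed secondary endpoints tested at 0.05. Section 1.3.2 makes the link between ongoing use and preparedness at 1 month a secondary objective. Section 2.6.3 says the trial's data will inform the larger trial, including its duration. A slope produced, or masked, by who chose to read would be weak evidence for that purpose.

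**Working it through.** **Inputs from the documents.** 50 enrolled, 90% (45) expected at V2 (sections 2.4.2 and 2.6.2); 1:1 allocation (2.5.3); two-sided 0.05 (2.6.3). Controls have no portal access to Take on Transplant before V2 (2.5.2), so time on it varies only within the intervention arm: 45/2 = 22.5, taken as n = 22.

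**Inputs assumed.** The documents give no correlations. The ranges used are 0.3 to 0.5 for literacy with use and with outcome, 0.3 to 0.5 in absolute value for use with baseline score, and 0.5 to 0.7 for baseline with V2 score.

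**The plan's own figure.** The only computed figure is the interval of 79-96% around 90% completion. A Wilson interval for 45/50 is 78.6 to 95.7%, which agrees. No power or precision is stated for any use-outcome model, so there is nothing further to reproduce.

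**Route 1, literacy as common cause, true effect of use zero.** If literacy has correlation a with use and with outcome, the spurious correlation is a × a.

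| a | Spurious r | False-positive rate, unadjusted | Adjusted for literacy |
|---|---|---|---|
| 0.3 | 0.09 | 7% | 5% |
| 0.5 | 0.25 | 20% | 5% |

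**Route 2, change score, true effect of use zero.** Let ρ be the baseline-to-V2 correlation and r_UB the correlation of use with baseline, with equal variances at both visits. Then

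corr(use, change) = r_UB (ρ − 1) / √(2 − 2ρ).

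For example, −0.3 × (−0.5) / √1 = 0.15.

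| ρ | r_UB | Spurious r | False-positive rate, unadjusted | Adjusted for V1 score |
|---|---|---|---|---|
| 0.5 | −0.3 | 0.15 | 10% | 5% |
| 0.5 | −0.5 | 0.25 | 20% | 5% |
| 0.7 | −0.3 | 0.12 | 8% | 5% |
| 0.7 | −0.5 | 0.19 | 14% | 5% |

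The rates come from simulation of normally distributed scores and were confirmed with 200,000 datasets per change-score scenario.

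**Reversing the sign.** With r_UB of +0.3 or +0.5, the spurious correlation changes sign (−0.12 to −0.25) and the two-sided error is the same. False significant slopes now run almost entirely the other way: a false positive slope appears in only about 0.1 to 0.7% of datasets. On CTF knowledge or Likert preparedness, a real benefit of use would then tend to be hidden. For Decisional Conflict, where a high score is unfavourable, the same reasoning holds with the scale turned round.

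**Putting the routes together.** If more literate people read more, and also start with higher knowledge, route 1 pushes the slope up and route 2 pushes it down. If people with low knowledge read more, route 2 pushes it up. The documents do not say which applies.

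**The case against.** The strongest reply is that these are pilot analyses and the plan claims little for them.

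- **The plan is silent on covariates.** Linear regression allows them, and a reader might wrongly infer that unadjusted models are prescribed. That correction stands. The silence still leaves the adjustment set to be chosen after the data are seen.
- **The Rationale is hedged.** It says what may appeal and what could explain, it speaks of shared decision-making in general, and it also notes that tailored interventions can help disadvantaged groups. It is too strong to say that the plan expects literacy to drive both use and benefit. The Rationale raises the possibility, which is enough to justify naming the covariate.
- **The dose-response label is narrow.** It applies only to the PrepDM models, which are marked exploratory. The change-score models are described as prediction, and section 1.3.2 speaks of association. No causal claim is made. This stands, and only the reporting rule remains to be written down.
- **Trial duration does not rest on these slopes.** The week-4 interview guide in Appendix 1 lists duration as a goal, and section 2.6.1 compares arms with 4 and 2 weeks of exposure. This stands.
- **The size is assumed.** At n = 22 the 95% interval around r = 0.15 is about −0.29 to 0.54 (Fisher transformation), so a design decision is unlikely to turn on a bias that small. This stands for correlations near 0.3.

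The literacy subgroup comparison in section 2.6.3 does not answer the point, because comparing changes between literacy groups does not adjust the slope on use.

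**Conclusion.** The point holds as one of possible bias in secondary and exploratory slopes. No baseline covariate is specified, use is self-chosen, and the synopsis itself names factors that may bear on both use and benefit. Under the assumed correlations, with zero true effect and about 22 participants, the false-positive rate is 8 to 20% for the change-score route and 7 to 20% for the literacy route. The lower ends belong to correlations of 0.3 and are modest. The 20% figures need 0.5, for which the documents offer no support.

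A reader might infer that a false benefit of use is the likely result. The documents do not support that: it requires low scorers to use the site more, and nothing in them says so. Nor is the randomised co-primary comparison of PrepDM touched.

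**What to change.** In sections 2.6.1 and 2.6.3:

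1. Fit each change-score model with the V1 value of that outcome (CTF knowledge, Likert preparedness or Decisional Conflict) and the S-TOFHLA score as covariates.
2. For PrepDM, which has no described V1 value, adjust for V1 Likert preparedness and S-TOFHLA score, in the secondary model and in the exploratory dose-response models.
3. Add education, as a single term, only in a sensitivity analysis, because the sample will not carry a long covariate list.
4. Report slopes with confidence intervals as associations, in line with the objective in section 1.3.2.

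The covariates are already part of the plan, so this is a change of wording. The cost is one or two degrees of freedom per model: with 22 participants, residual degrees of freedom fall from 20 (intercept and time) to 18, or 17 with education. Two limits remain. V1 Likert preparedness is only a stand-in for a baseline PrepDM, and unmeasured motivation can still confound the slopes, which is why the fourth step is needed even after adjustment.

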1.3. Objectives of the clinical investigation

1.3.1. Primary objective

The primary research objectives are to pilot test feasibility and efficacy of ToT to improve patient preparedness for decision making about LTx. The co-primary endpoint is feasibility, which will be defined successful by 90% of enrolled participants completing the 2-week study visit. A co-primary endpoint is an intention-to-treat assessment of the difference in mean PrepDM Scale in the intervention versus control arms of the study at the 2-week study visit.

1.3.2 Secondary objective(s).

The secondary objectives are to:

- Understand LTx knowledge gained.
- Assess changes in decisional conflict.
- Measure changes in preparedness for LTx discussions.
- Assess changes in depression and anxiety symptoms.
- Longitudinally characterize time spent using ToT through analysis of patient-level usage data and determine whether ongoing use of the tool is associated with maintaining or increasing ratings of preparedness at 1-month.
- Identify baseline demographic and health literacy predictors of increased ToT usage
- Analyze interview transcripts to inform revision of ToT prior to a large randomized controlled trial

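### The co-primary compares PrepDM at 2 weeks between arms that saw different websites, with no stated referent and no baseline, so it shows relative perceived preparation and not, by itself, a rise in patient preparedness

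*Combined protocol and SAP*

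**What the plan says.** The efficacy co-primary in section 2.6.1 is the "difference in mean PrepDM Scale in the intervention versus control arms of the study at the 2-week study visit". Section 2.6.3 says that it "will be assessed using linear regression, with statistical significance level set at 2-sided alpha <0.05", and names no covariates. Neither section says which website a participant is to have in mind when answering PrepDM at V2.

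Section 2.5.2 states that "participants will be randomized to first receive access to only one of the two websites through the portal". Section 2.5.3 adds when this ends: "After the 2-week session interview, access to the opposite arm assignment will be unlocked".

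A later secondary endpoint in section 2.6.1 does name a referent: "The PrepDM Scale will be measured for all participants with respect to Take on Transplant". That comparison sets 4 weeks of exposure against 2, so it belongs to the 4-week visit, when both arms have had Take on Transplant.

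The primary objective in section 1.3.1 is "to pilot test feasibility and efficacy of ToT to improve patient preparedness for decision making about LTx". Aim 1 in the synopsis likewise asks whether the tool improves patients' preparedness for transplant discussions.

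Section 2.6.1 also compares Likert preparedness between arms as a V2 mean, and Decisional Conflict as change from baseline to V2. A change in Likert preparedness from baseline appears only in the analysis of website usage, but it shows that a V1 value is collected.

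**The concern.** The objective concerns a state of the patient. The synopsis rationale, however, describes PrepDM as used in evaluating a decision support tool. In the usage analysis of section 2.6.1, PrepDM enters as a 2-week mean, while knowledge, Likert preparedness and decisional conflict enter as changes from baseline. Both facts suggest a score taken after exposure and tied to a resource. If so, at V2 the intervention arm answers about Take on Transplant, and the only study website that controls can answer about is unos.org.

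The two arms could then differ in how far they credit their own site while differing less, or not at all, in how prepared they are. Nothing in section 2.6.3 links the secondary endpoints to the efficacy statement. The results are meant to inform a larger trial, so an over-read endpoint could be carried forward.

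**Working it through.** **1. The plan's own figure.** The only sizing figure (section 2.6.2) is 90% of 50 completing V2, 95% CI 79–96%. The Wilson interval with p = 0.90, n = 50, z = 1.96 (z² = 3.84):
- Centre: (0.90 + 3.84/100) / (1 + 3.84/50) = 0.9384 / 1.0768 = 0.871.
- Half-width: 1.96 × √(0.90 × 0.10/50 + 3.84/(4 × 50²)) / 1.0768 = 0.085.
- Interval: 78.6% to 95.7%, which rounds to the stated 79–96%.

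No numerical error is alleged. No PrepDM SD, target difference or power is given.

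**2. What each measure is tied to.**

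| Measure | Time compared | Referent in the documents | Baseline in the arm comparison |
|---|---|---|---|
| PrepDM, co-primary | V2 | not stated; one site open per participant | none |
| PrepDM, secondary | 4 weeks | Take on Transplant, both arms | none |
| Likert preparedness | V2 | no website in the endpoint definition | none named, though V1 is collected |
| Decisional Conflict | V2 | no website in the endpoint definition | change from V1 |

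The referent is fixed for the secondary PrepDM and left open for the co-primary. The 4-week sentence shows that PrepDM can be tied to a named site. It does not establish the V2 referent, which remains an inference from access.

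**3. How easily a site-linked difference could be significant (illustration).** Section 2.4.2 expects 45 completers, and allocation is 1:1 (section 2.5.3), so take 22 and 23. Suppose preparedness is equal and PrepDM differs by d SD only through the site being rated.
- SE of the difference in SD units: √(1/22 + 1/23) = 0.298.
- Normal approximation for 80% power, two-sided 0.05: d = (1.96 + 0.84) × 0.298 = 0.84. The two-sample t-test gives 0.855.
- At d = 0.5: 0.5/0.298 = 1.68, and Φ(1.68 − 1.96) = 0.39. The t-test gives 0.374.
- In points, assuming an SD of 15 to 30: 0.855 × 15 ≈ 13 to 0.855 × 30 ≈ 26.

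This is an ordinary power curve that holds for any endpoint of this size. It is not evidence that such a difference exists.

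**4. Likert scoring.** Don't know is coded 0, below not at all prepared at 1. A move from the first to the second adds 1 − 0 = 1 point, the same as a move from moderately to very prepared (4 − 3 = 1). A response that expresses uncertainty is thus scored as the least prepared state.

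**The case against.** The strongest reply is randomisation. Participants who were already well prepared are balanced between arms in expectation, so the missing PrepDM baseline costs precision and does not bias the contrast. A V2 difference does support a relative effect of Take on Transplant versus unos.org on perceived preparation, which is what a trial with an attention control asks. This stands.

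A reader might infer that the co-primary shows only which site was found more helpful or better liked. The documents do not support that. They do not reproduce the PrepDM items, they call the scale a validated measure of preparedness, and section 2.6.1 defines high scores as greater perceived preparation. A reader might also take the sentence naming Take on Transplant as proof of the V2 referent, but it belongs to the 4-week comparison.

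It can also be said that the plan already compares knowledge, decisional conflict and Likert preparedness between arms, and nowhere says that PrepDM alone will decide the matter. That is true, but none of them is given a role in interpreting the co-primary.

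Nor is the Likert item clearly free of the site. Its survey wording is not shown, and question 13 of the week 2 interview guide (Appendix 1) asks about preparedness after using the website, with Likert probes. The item is useful support and not an arbiter. A rule that improvement is claimed only if the Likert estimate has the same sign would be weak: with no true Likert effect the sign agrees about half the time by chance, and more often if the two scores correlate.

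**Conclusion.** The point holds in a limited form. The V2 PrepDM referent is unstated, the arms have had portal access to different sites, and no PrepDM baseline is used. The co-primary estimates perceived preparation after Take on Transplant relative to unos.org, probably as attributed to the assigned site. It does not by itself show that preparedness rose from baseline.

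How much of a PrepDM difference would be site-linked cannot be determined from the documents; the 80% and 37% figures only show scale. The conclusion assumes that participants use the portal as described and that PrepDM at V2 is answered about the assigned site. The second assumption is likely from the rationale and the access rules but is not stated. This is a free improvement in wording and analysis, between optional and recommended, and gives no ground for replacing the endpoint.

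**What to change.** - Keep PrepDM as co-primary. In sections 2.6.1 and 2.6.3, state which website it refers to at V2 in each arm.
- Describe its result as perceived preparation for decision making from the assigned website, Take on Transplant relative to unos.org. Do not recast it as helpfulness.
- In section 2.6.3, analyse V2 Likert preparedness by linear regression on arm adjusted for its V1 value, in place of the comparison of V2 means with no named adjustment. Give the item's wording at both visits.
- In that analysis, do not score don't know as 0. State in advance how it is handled and report its frequency by arm.
- Name this analysis, with Decisional Conflict Scale change, as the pre-specified support for any statement about patient preparedness. Report all three estimates side by side with 95% CIs, without a same-direction rule.

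The cost is a few sentences in the endpoint and analysis sections; no new data are needed. The drawback is a narrower claim if only PrepDM differs.
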